- The estrogen cream used in the study is similar to the FDA approved estradiol vaginal cream (ESTRACE). When estrogen cream is placed deep in the vagina in the same dose as the study cream, absorption is low and for most women blood levels remain the same as for those not using estrogen cream. If absorption takes place, side effects may include:
- Most Common:
 - Headache (13%)
- Less Common (1-10%):
 - Hot flushes
 - Breast tenderness
 - Vaginal infection (yeast infection, bacterial infection)

- Vaginal pain/discomfort
- Vaginal spotting
- Gastrointestinal complaints (abdominal pain, nausea, diarrhea)
- Urinary tract infection
- Hair loss
- Insomnia
- Anxiety
- Dizziness
- Changes in libido
- Back and joint pain
- Respiratory tract infection
- Discoloration of the skin
- Rare but Serious Side Effects (<1%)*
 - Endometrial cancer
 - Estrogen therapy may cause the lining of the uterus to grow and can increase the risk of uterine cancer. Because the amount of estrogen absorbed is low when using topical estrogen cream, the risk for uterine cancer is lower than when taking oral estrogen. You will have pelvic ultrasounds throughout the study to monitor the lining of the uterus.
 - Breast cancer
 - Estrogen therapy is associated with a small increased risk of breast cancer.
 - Cardiovascular disease
 - Estrogen therapy has been shown to increase the risk of heart disease including heart attack, stroke, and serious blood clots in some women.
 - Dementia
 - An increased risk of developing probable dementia in postmenopausal women 65 years of age or older has been reported in women receiving oral estrogen alone or estrogen combined with progestins.
 - As with any drug, allergic reactions may occur due to the study drug. These may range from mild to severe, can be life-threatening/fatal and include hives, difficulty breathing, and swelling of your face, lips, tongue, or throat. You should seek emergency medical treatment should you experience an allergic reaction.

b. Potential Benefits to Subjects

Subjects will be entering the study because they experience pain with sexual intimacy. There is a greater than 50% probability that they will experience lessening and even correction of their dyspareunia by study completion, since all will get study drug, which is the known therapy for this problem. All will apply study drug to the specific site of tenderness and is hypothesized to increase the likelihood of benefit. If the intervention is successful for them, they can continue to use the intervention regimen once the study is completed, providing a benefit. All subjects will be offered the option to receive information about the outcome of the study once it is completed, analyzed and published in a peer review journal and the information may benefit each of them.

It is possible that the gynecologic screening via ultrasound may uncover a condition for which timely intervention is beneficial to the subject. The possible findings would include intrauterine polyps or thickened endometrium that could be pre-cancerous. The potential benefit is great if cancer might be prevented.

Subjects may experience psychological benefits in relation to their sexual function and sexual relationship by exploring their issues and having a source of expert information about dyspareunia and vulvar pain in the study staff.

16. Drugs or Devices

There will be neither a new drug application nor a premarket approval application as we are using an FDA approved drug, Lidocaine 4% topical solution, NDC # 0054-3505-47.

We will follow Research Pharmacy policies & procedures for the compounding, randomization and dispensation of study drug.

Drug will be dispensed by the research pharmacy to study staff and study staff will dispense study drug directly to subjects. Subjects will be requested to return any unused drug.

REFERENCES

- ACOG. Diagnosis and Management of Vulvar Skin Disorders. ACOG Practice Bulletin #93, 2008
- ACOG Committee Opinion: The Use of Vaginal Estrogen in Women With a History of Estrogen-Dependent Breast Cancer. Number 659, March 2016.
- Brubaker, L. and A.J. Wolfe, *The new world of the urinary microbiota in women.* Am J Obstet Gynecol, 2015. **213**(5): p. 644-9.

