Treating Where it Hurts: A randomized blinded clinical trial of local estrogen to the vulvar vestibule for dyspareunia in postmenopausal women

NCT03240081

13MAR2019

Principal Investigator: [name], MPH

eIRB #: 16770

1. Protocol Title

Treating Where it Hurts: A randomized blinded clinical trial of local estrogen to the vulvar vestibule for dyspareunia in postmenopausal women

2. Objectives

Purpose:

To perform a pilot study to evaluate the efficacy and safety of local estrogen therapy applied to the vulvar vestibule in a cohort of postmenopausal women with moderate or severe dyspareunia, and to examine the microscopic features of this condition before and after local estrogen therapy.

Primary goals:

- 1. To compare serum levels of β -estradiol before and during paired dosing of the hormone to the vulvar vestibule nightly.
- 2. To assess the comparative treatment efficacy of two strengths of β -estradiol dosed at an increased frequency to the vulvar vestibule.
- 3. To assess and characterize the microscopic features of tender vulvar vestibule tissues in postmenopausal women who have moderate to severe dyspareunia acquired since menopause.
- 4. To assess whether β-estradiol cream applied nightly for three months to the vulvar vestibule normalizes the microscopic profile of vestibule findings in parallel with correction of dyspareunia.

Hypotheses:

- 1. Topical estrogen to the vulvar vestibule is safe
 - a. β-estradiol serum levels associated with nightly estrogen applications to the vulvar vestibule will not be significantly different than levels published in studies of vaginal applications.
- 2. This condition is a form of vestibulodynia and will regress with topical estrogen therapy
 - a. For postmenopausal women with significant coital pain, vestibule biopsies will show neural hyperplasia and an infiltrate of lymphocytes, hallmarks of localized provoked vulvodynia, and doses of topical β -estradiol will be effective when applied to the zone of tenderness, the vestibule.
- 3. Nightly therapy to the vestibule will be more efficacious than published results of standard semiweekly vaginal therapy.
 - a. Nightly therapy will effect a correction of moderate/severe dyspareunia in greater than 62% of subjects, a published rate of correction using the standard treatment frequency to the vagina.

Primary endpoints:

- 1. Serum levels of β -estradiol before and during treatment with two strengths of cream applied locally to the vestibule.

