- 2. Measurements of endometrial thicknesses in subjects with a uterus at study end, comparing results to baseline measurements.
- 3. Changes in tissue lymphocyte densities and neuronal hyperplasia comparing baseline to study end.
- 4. Levels of dyspareunia measured by the Numerical Rating Scale (NRS) during regimens of nightly estradiol therapy applied to the vulvar vestibule, determining how soon and how uniformly this schedule corrects painful penetration in study subjects.

Secondary endpoints:

- 1. Pain descriptors as measured by the modified Vulvar Pain Assessment Questionnaire—screen (VPAQ-screen) (Dargie, 2016)
- 2. Sexual function evaluated using the validated but modified VPAQ-Screen.
- 3. Sexual distress as measured by the (VPAQ-Screen).
- 4. Lower Urinary Tract symptoms (LUTS) of menopause as measured by a set of validated questions.
- 5. Vestibular tenderness as measured clinically by the cotton swab touch test and the lidocaine test.
- 6. Vaginal and vestibular atrophy as measured by visual examination and pH of the vaginal secretions.
- 7. Characterization of the urogenital microbiome via swabs collected from the vestibule and vagina.

3. Background

Pain with sex is a common problem experienced by women after the age of menopause, and it is commonly termed "vulvovaginal atrophy" or "vaginal dryness" by most clinicians (ACOG, 2008). Genitourinary Syndrome of Menopause (GSM) is the new term put forth by two professional societies (Portman, 2014). Vulvar complaints develop in association with loss of ovarian estrogens, and the prevalence of sexual pain in women over 50 is 50% (ACOG, 2008). Symptoms are chronic and tend to worsen over time (Gass, 2013). The relationship of vulvar symptoms to sexual difficulties is well established (Simon, 2014). However, the research into this problem is variable in its focus, and there are many gaps.

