Whereas our prior RCT provided convincing data that the location of pain in postmenopausal dyspareunia is the vulvar vestibule, and that a non-hormonal therapy can be an effective palliative option, there is a major unmet need for data about corrective therapy. The only curative therapy for noxious postmenopausal vulvar symptoms is estrogen (Gass, 2013). Various female populations are in need of more complete information about risks and benefits of local estrogen therapy, as safety is a concern for both women who have no contraindication to estrogen and those who must balance risks of cancer recurrence. Herbenick documented that most young survivors of breast cancer wish for effective sexual enhancement products, demonstrating an unmet need in this population (Herbenick, 2008). That population presently numbers over 3 million women in the US (Natl Cancer Institute, 2013). A very recent ACOG Committee Opinion suggesting that vaginal estrogen therapy should be considered in survivors of estrogen-dependent breast cancer whose pain is refractory to non-hormonal remedies, because data does not show that use of local estrogen elevates rates of breast cancer recurrence (ACOG, 2016). This expert opinion, drawn from limited data on post-cancer vaginal estrogen, is an acknowledgement of the magnitude of the unmet need for effective therapy for dyspareunia in this breast cancer population. Our study will compare the serum levels achieved by vestibule dosing to serum levels from existing publications on the safety profile of estrogen products applied to the vagina.

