The study will include 50 subjects affected by dyspareunia and 5 reference cases (Total N=55). We estimate a need to screen 60 women in order to enroll 50 patients and we arrived at this estimate using the following considerations. We assume that all potential subjects who pass the phone screening and come for a screening examination having the complaint of postmenopausal dyspareunia will be found to have tenderness in the vulvar vestibule, as found in 100% of screened women in our previous study to locate the site of genital tenderness in a similar population (Goetsch, 2014). The prediction of how many women may be eliminated at screening comes from cautions regarding uterine issues. Although prior studies have indicated that use of local estrogen is without risk of stimulation to the uterus, we will be studying doses to an anatomic area with no prior data on absorption. We therefore feel it is important to screen candidates with a uterus to ensure that they enter the study with no evidence of thickening of the uterine lining, which can predispose to endometrial cancer. In women with a uterus, we will assess the width of endometrial stripes by transvaginal ultrasound. A 2011 British study of transvaginal endometrial screening found that 10-20% of asymptomatic women had a stripe width of 5 or more. (Jacobs, 2011) Those with a stripe ≥5mm will be excluded. The Oregon obesity prevalence is 29% (StateofObesity.org), defining a population at increased risk for endometrial thickening from adipose-related estrogen unopposed by any progestin. From a 2012 publication reporting the number of women in a Kaiser Permanente Northwest population who have had hysterectomies, we hypothesize that 26% of women screened will not have an intact uterus. (Lacie, 2012) Calculating the excess screens needed due to thickened endometrium in obese women and considering the proportion likely to have had hysterectomies, an estimated 60 women will be screened to enroll 50 subjects. All will be in the OHSU cohort.

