 - O Diary questions include pain scoring of either a Tampon Test (a validated test used to assess vestibular tenderness), or a sexual penetration encounter

Visit 3 (12 hour blood draw +/- 60 minutes)

• Blood sample collection for serum β-estradiol [12 hours after the initial study drug dose (8 or 9am after an initial dosing at 8 or 9pm the evening before)]

Visit 4 (week 4 +/- 3 days)

- Update to medical and medication history
- Review of possible symptoms associated with study drug
- Collection and review of diary, additional pages dispensed as needed
- Pelvic examination to assess genital atrophy and vestibule tenderness
- Blood sample collection for serum β-estradiol
- Completion of questionnaire, VPAQ #2

Visit 5 (week 8 +/- 3 days) – telephone or email contact only

- Update to medical and medication history
- Review of possible symptoms associated with study drug
- Review of diary

Visit 6 (week 12 +/- 3 days)

- Update to medical and medication history
- Review of possible symptoms associated with study drug
- Collection and review of diary
- Pelvic examination to assess genital atrophy and vestibule tenderness
- Collection of swabs from the vestibule and from the vaginal side walls for later analysis of the microbiome composition.
- Repeat transvaginal ultrasound to assess endometrial stripe thickness
- Blood sample collection for serum β-estradiol
- Completion of questionnaires: VPAQ #3 and LUTS questionnaire
- Remaining study medication collected from participant by study staff
- Repeat vulvar biopsy (for those subjects enrolled in the sub-study)

Visit 7 (follow-up)

• Subjects will be contacted by phone, mail or email 4 months after study completion to ask the status of their dyspareunia and estrogen regimens and to administer follow-up questionnaires (VPAQ modified + LUTS questionnaire).

Long-term follow up

Study staff may request permission to contact subjects by telephone or email for up to 5 years to ask the status of their pain and any medication they are using to treat their pain.

Duration of Participation:

The duration of active participation will be 12 weeks and limited further data will be obtained from a phone call, mail, or electronic communication 7 months after enrollment into the study. Participants may be asked to allow additional follow-up contact for up to 5 years after their last study visit.

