Participation for reference group subjects will last the duration of Visit 1. There will be no follow up of reference subjects.

Genetic Testing:

No human genetic testing or collection of human genetic information is involved in this study. Ribosomal RNA will be analyzed from resident vaginal and vestibular microbes.

10. Study Drug

The study drug will be compounded β -estradiol, an FDA approved medication. It will be compounded by Lloyd Center Pharmacy, which has a long history of collaboration with the OHSU Research Pharmacy. They adhere to the standards of the US Pharmacopeial Convention (USP), a 194 year-old scientific organization that sets standards for medication purity; in the US the FDA enforces these standards. Lloyd's adheres to Chapters 797 (sterile medications) and 795 (non-sterile medications) of the USP, and the β -estradiol cream, being a non-sterile product, will adhere to standards set out in Chapter 795.

Subjects will be randomized to receive one of two strengths of compounded β -estradiol cream: 100mcg or 50mcg/0.5 gram. Each subject will be issued a pump that will dispense 0.5cc (0.5gm) of study drug with each pump action. They will be instructed in application of the cream to the vulvar vestibule on a nightly basis. They will be asked to keep a diary record of drug applications.

The β -estradiol cream will be twice the strength of the recommended FDA-approved strength so as to be able to dose half the amount for purposes of patient acceptability. Too much cream would likely elicit complaints of messiness and excess discharge. The base study cream will be Versabase, a well-known and well-absorbed base for compounded vaginal medications. It is free of propylene glycol, a preservative found in the base used in the proprietary vaginal creams, known to be an irritant to the vestibule.

Subjects, investigators and personnel will be blinded as to the randomization, as the OHSU research pharmacy will make the assignments. We will request that subjects bring remaining study medication to their final study visit (Visit 6) for collection by study staff so dosing may be confirmed after analysis, if needed.

11. Data and Specimens

a. Handling of Data and Specimens

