Fifty women who are postmenopausal, have moderate or severe entry dyspareunia and meet Friedrich's criteria for vestibulodynia will be recruited into the study. We are assuming a baseline pain score of 70 ± 21.5 (mean \pm std) from a previously reported study of a mixed group of treated and untreated postmenopausal patients with dyspareunia, (Kao, 2012), and we assume a 30% treatment effect after four weeks with the lower-dose intervention drug. A sample size of 50, divided into two arms, allowing for a 10% drop out rate in each of two arms, will achieve >85% power to detect at least 20 points mean difference in dyspareunia pain scoring between the two intervention drug strengths at 4 weeks, with an alpha level of 0.05 for two-sample t-test.

The tissue biopsy sub-group will be 10 subjects from each intervention arm (n=20), and using a one-sided exact test with alpha level of 0.05, this number of subjects will achieve 80% power to detect a difference of 15.6% in inflammation, assuming the baseline proportion of moderate or strong inflammation is 95%. (Leclair, 2013). Patients' biopsies at 3 months will be compared to their baseline biopsy.

To establish a reference group of biopsy specimens, we wish to seek out 5 subjects to fulfill the exploratory aim of assessing the histologic profile of vestibule tissues in postmenopausal women who are not on estrogen and do not have penetrative pain. The prevalence of this type of patient has not been established. We would expect them to have atrophy but no vestibular inflammation or neural hyperplasia. They will not technically be "controls" for purposes of this study. As there are no published studies analyzing the histologic character of the vestibule in such women, the small exploratory number (n=5) does not allow a power analysis. We will recruit these subjects with the help of our Urogynecology colleagues who are doing a study on the vaginal/bladder microbiome and are screening postmenopausal patients.

Swabs with material for microbiome analysis will be analyzed with the help of the Urogyn bioinformatics specialist using QIIME bioinformatics software.

13. Privacy, Confidentiality, and Data Security

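### Hypothesis 1a is met by a non-significant difference in serum estradiol from published vaginal levels, and Section 12 plans no serum analysis that would show what the data can exclude

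*Combined protocol and SAP*

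**What the plan says.** Section 2 (Hypotheses) opens with the statement "Topical estrogen to the vulvar vestibule is safe". Its only lettered item, 1a, predicts that serum estradiol under nightly vestibular application "will not be significantly different than levels published in studies of vaginal applications". No margin or interval is attached.

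Serum estradiol before and during treatment is primary goal 1 and primary endpoint 1. Section 3 (Background) says "Our study will compare the serum levels achieved by vestibule dosing to serum levels from existing publications", and its closing paragraph adds that the study will establish how much low-dose estrogen is absorbed from the vestibule. No published series, product, dose or reference value is named.

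Section 9 schedules serum draws at Visits 1, 3, 4 and 6. Visit 3 is timed at "12 hours after the initial study drug dose"; Visits 4 and 6 state no time since application. Section 11 covers storage and batch assay. Section 12 (Data Analysis) covers pain power, biopsy power, the five reference cases and microbiome software, and does not mention serum estradiol.

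Safety is also addressed elsewhere. Primary endpoint 2 is "Measurements of endometrial thicknesses in subjects with a uterus at study end", compared with baseline. Symptoms are reviewed at Visits 4 to 6, and Section 14 refers to a separate Data Safety Monitoring Plan, which was not available for this review.

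**The concern.** Failing to find a difference is not evidence that two levels are alike. If 1a is judged as worded, its chance of being met rises as the sample shrinks or the measurements become noisier, which is the wrong direction for a statement placed under a safety heading.

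An analysis section can repair such wording by committing to an estimate, an interval and a named comparator. Section 12 does not do so for serum estradiol, although it is a primary endpoint. At stake is the exposure conclusion: 1a could be called met while the data still allow a small-to-moderate excess over vaginal use. Section 3 gives the serum comparison weight, because it presents it while discussing the safety concerns of women who use local estrogen, including those balancing a risk of cancer recurrence.

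**Working it through.** **The plan's own figure.** Section 12 states more than 85% power for a 20-point pain difference with SD 21.5, alpha 0.05 and 50 women in two arms, "allowing for a 10% drop out rate in each of two arms". Assuming equal arms, 25 × 0.9 = 22.5, taken as 22 per arm. Noncentrality = 20 / (21.5 × √(2/22)) = 3.085, df = 42, two-sided critical t = 2.018, power = 85.4%. The figure reproduces, but it concerns pain and says nothing about serum.

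**Inputs for serum.** The documents give no serum SD, no reference mean and no size for the published series, and 1a does not say whether it applies per strength or pooled. The illustration therefore works in SD units and assumes a two-sided 5% t-test, 22 women in one arm, and a true excess of d SDs over vaginal use.

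**Case A: published mean treated as fixed (favourable).** P(non-significant) = P(|T| < t*), where T is noncentral t with n − 1 df and noncentrality d√n. For n = 22, t* = 2.080.
- d = 0.5: noncentrality 0.5 × √22 = 2.345; P = 0.391.
- d = 0.8: noncentrality 0.8 × √22 = 3.752; P = 0.053.

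**Case B: published series of 50 women with the same SD (assumed).** Noncentrality = d / √(1/22 + 1/50) = d / 0.2558, df = 70, t* = 1.994.
- d = 0.5: noncentrality 1.954; P = 0.513.
- d = 0.8: noncentrality 3.127; P = 0.131.

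**Sensitivity at d = 0.5.** With a published series of 20 or 100 women in place of 50, P is 0.648 or 0.442 for n = 22. If both strengths are pooled (n = 45, which assumes one common mean and SD), P is 0.093 in Case A and 0.327 in Case B.

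**What an interval would show.** The 95% CI half-width for one arm is t*/√n = 2.080/√22 = 0.44 SD. A bare report of no significant difference conceals this width.

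**The case against.** The strongest reply is that 1a is only a prediction. The comparison promised in Section 3 has no test attached and could be purely descriptive; primary goal 1 and primary endpoint 1 are before-and-during comparisons, which are sound. This stands in part. A reader might infer that the investigators intend to report a non-significant test as proof of safety, but nothing in the documents says so. What remains is a prediction whose stated criterion is non-significance, with no planned analysis to prevent it being read as similarity.

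A reader might also infer that serum is the trial's only safety evidence. It is not: endometrial thickness, symptom review and the separate monitoring plan exist. Those described here do not answer how serum exposure compares with vaginal use.

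A third tempting step is to cite Section 5, which says "we will be studying doses to an anatomic area with no prior data on absorption", as showing that the serum result must carry the exposure judgement. There the sentence justifies ultrasound screening of the endometrium. The link between serum and absorption comes from Section 3.

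It is also fair to say that the SD-unit figures have no clinical anchor. Nothing in the documents shows whether 0.3, 0.5 or 0.8 SD matters, so the figures show how the criterion behaves and do not establish that a relevant excess would be missed.

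Finally, this is a pilot, and a powered equivalence test would be out of proportion. That is accepted. It is a reason to report estimates with intervals, which is all the fix asks for.

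**Conclusion.** The concern holds in this form: the only sub-hypothesis under the safety heading is met by non-significance, and Section 12 contains no serum analysis for a primary endpoint. Both facts can be read directly from the text and need no assumption.

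The size is illustrative. With 22 women in an arm, 1a would be called met despite a true 0.5 SD excess about 39% of the time against a fixed published mean and 51% against an assumed series of 50. For a 0.8 SD excess the figures are 5% and 13%, so the weakness concerns small-to-moderate excesses. These results rest on equal arms, the 10% dropout stated for the pain calculation, a two-sided 5% t-test and equal SDs. Pooling the strengths lowers them and a smaller published series raises them. The point should be fixed, but it does not undermine the trial's design or its before-and-during serum comparison.

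**What to change.** Reword 1a along these lines: *Serum estradiol during nightly vestibular application will be estimated with 95% CIs and described beside levels from a named published series of vaginal application.*

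Add to Section 12: *For each strength, on-treatment estradiol and its ratio to baseline will be reported with 95% CIs at each draw, beside the named series and its own uncertainty; a non-significant difference will not be taken as evidence of similarity or safety.*

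Optional, and separate from the main fault: Section 10 says of participants "They will be asked to keep a diary record of drug applications". The diary form is not in the supplied text. If it does not already capture the time of the last application before the Visit 4 and Visit 6 draws, adding it would help when those levels are set beside published ones.

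The cost is one reworded sentence, one analysis paragraph and slightly more analysis, with no added women, visits or samples. The downside is that a claim of similarity to vaginal use becomes harder to make, since one arm's interval extends about 0.44 SD either side of the estimate even before the published series' own uncertainty is counted.

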Women's search for estrogen products that promise safe risk profiles is indicated by the number of women ordering estrogen products from compounding pharmacies. This has bearing on our proposal because we plan to work through the OHSU Research Pharmacy with Lloyd Center Pharmacy to formulate the intervention medications in this study. Lloyd Center Pharmacy has years of experience with compounded formulations of local estrogens. The North American Menopause Society Advisory Panel published data from a national population study demonstrating that 28% of US estrogen-users obtain their medications from compounding pharmacists. Women perceived the compounded versions as safer because they are "natural" and "bioidentical" (Pinkerton, 2015). In our practice we also encounter many women who feel they cannot afford the FDA-approved estrogen products, and they are open to getting a less expensive prescription from a compounding pharmacy.

There are many remaining gaps in current knowledge regarding postmenopausal dyspareunia. Our RCT was the first to draw attention to the vulvar vestibule in women with postmenopausal dyspareunia. We chose to study the population of women with no estrogen because they would represent the purest examples of estrogen lack for reasons of ovarian senescence and their cancer history. This project will focus on a larger population of postmenopausal women who can use estrogen. This project will add additional needed data regarding the prime location of tenderness. We aim to ascertain whether local estrogen therapy works more effectively when applied to the actual location of allodynia. By studying a postmenopausal population, we can advance knowledge about the vulvar vestibule and efficacy of local estrogen therapy.

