This will be a novel study in several ways. It will ascertain the absorption of low dose estrogen from the vulvar vestibule. It will study whether there is a relative therapeutic benefit to applying local estrogen to the location that hurts in cases of postmenopausal dyspareunia. It will be the first study to gauge therapeutic efficacy of local estrogen by paring physical findings in the pain location with validated measures of dyspareunia. It will be the first study to evaluate paired microbiome samples of the vulvar vestibule and vagina in postmenopausal women. It will be the first study to vary the estrogen dosing to specifically reduce pain rather than reduce measures of atrophy. It will be the first study to assess vestibule histology before and after a therapeutic intervention known to correct dyspareunia.

4. Study Design

This will be a prospective, randomized, double blind intervention pilot study that will compare two strengths

of β -estradiol applied nightly to the vulvar vestibule for three months in women with moderate or severe postmenopausal dyspareunia. Treatment efficacy and safety parameters as well as tissue histology will be assessed.

5. Study Population Number of Subjects

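### Hypothesis 3/3a claims an advantage over published vaginal therapy on a rate above 62%, with no test or interval planned and no arm dosed vaginally or semiweekly

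*Combined protocol and SAP*

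**What the plan says.** Section 2 (Objectives) states as hypothesis 3: "Nightly therapy to the vestibule will be more efficacious than published results of standard semiweekly vaginal therapy". Sub-item 3a gives the only quantity attached to it, namely "correction of moderate/severe dyspareunia in greater than 62% of subjects, a published rate of correction using the standard treatment frequency to the vagina". No reference accompanies the 62%. The related primary endpoint (number 4) is the NRS pain level, "determining how soon and how uniformly this schedule corrects painful penetration in study subjects". It gives no NRS value that counts as correction.

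Section 4 describes a randomised, double-blind pilot of two estradiol strengths "applied nightly to the vulvar vestibule for three months in women with moderate or severe postmenopausal dyspareunia". Section 10 confirms that both strengths are applied nightly to the vestibule, and Section 15b says every woman receives study drug.

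Section 12 contains two powered comparisons. One is a two-sample t-test, with more than 85% "power to detect at least 20 points mean difference in dyspareunia pain scoring between the two intervention drug strengths at 4 weeks". The other is the biopsy comparison, "using a one-sided exact test with alpha level of 0.05". Neither concerns the 62%. No interval, analysis set, pooling rule or missing-data rule is given for 3a.

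Section 3 adds two statements about site: "We aim to ascertain whether local estrogen therapy works more effectively when applied to the actual location of allodynia" and "It will study whether there is a relative therapeutic benefit to applying local estrogen to the location that hurts in cases of postmenopausal dyspareunia".

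**The concern.** A comparative claim rests on a single proportion and a fixed external number. Two things are missing.

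- **Allowance for sampling error.** With about 50 women, an observed rate modestly above 62% is what chance often produces when the true rate is 62%.
- **A within-trial comparator.** Site and frequency are the same in both arms, so no contrast inside the trial bears on either. Differences from the published source in population, cream base, outcome definition or follow-up would be mixed in with any treatment difference.

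At stake is a published statement that nightly vestibular dosing outperforms vaginal dosing. It could rest on a result compatible with 62%, in a study where no woman was dosed vaginally.

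The rate itself is also not fully defined. The time point is partly given: three months in primary goal 4, and study completion in Section 15b. Still open are the NRS cut-off, whether a tampon or an intercourse score decides (the Visit 2 diary in Section 9 accepts either), and whether the denominator is all randomised women or those who complete.

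**Working it through.** **Inputs.** From the plan: benchmark p0 = 0.62 (hypothesis 3a); N = 50 in two arms with 10% dropout, so 50 × 0.9 = 45 completers; SD 21.5, difference 20, alpha 0.05 (all Section 12). Assumed: 1:1 allocation, a two-sided t-test, both arms pooled for 3a, and 62% treated as known without error.

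**1. The plan's own power figure.** Completers per arm are 25 × 0.9 = 22.5, so take 22 and 23. The noncentrality is 20 / (21.5 × √(2/n)).
- n = 22: noncentrality 3.085, df 42, power 85.4%.
- n = 23: noncentrality 3.155, df 44, power 87.0%.

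The stated figure of more than 85% reproduces. It answers a different question: strength against strength, mean score, week 4.

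**2. Comparing the observed rate with 62%.** The smallest counts above 62% are 32/50 (64.0%) and 28/45 (62.2%). With X ~ Binomial(n, p):

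| True rate | P(X ≥ 32), n=50 | P(X ≥ 28), n=45 |
|---|---|---|
| 55% | 0.127 | 0.206 |
| 62% | 0.447 | 0.554 |

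**3. Exact (Clopper-Pearson) two-sided 95% intervals.**

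| Count | Rate | Interval |
|---|---|---|
| 32/50 | 64.0% | 49.2–77.1% |
| 35/50 | 70.0% | 55.4–82.1% |
| 38/50 | 76.0% | 61.8–86.9% |
| 39/50 | 78.0% | 64.0–88.5% |
| 28/45 | 62.2% | 46.5–76.2% |
| 34/45 | 75.6% | 60.5–87.1% |
| 35/45 | 77.8% | 62.9–88.8% |

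The first counts whose lower limit exceeds 62% are 39/50 and 35/45. At a true 62% they are reached with probability 0.012 and 0.019.

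**4. Results that meet 3a but remain compatible with 62%.** For n = 50 this band is 32 to 38.
- True rate 62%: 0.447 − 0.012 = 0.435 (0.4345 before rounding), about 43%.
- True rate 70%: 0.859 − 0.139 = 0.720, or 72%.

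**5. Power of the interval rule.**

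| True rate | 39/50 | 35/45 |
|---|---|---|
| 70% | 14% | 16% |
| 75% | 38% | 41% |
| 80% | 71% | 72% |

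**6. Denominator.** The same 28 corrected women are 28/45 = 62.2% of completers but 28/50 = 56.0% of those randomised (interval 41.3–70.0%). This illustration assumes that none of the five dropouts was corrected.

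**7. Counting dropouts as not corrected.** If each woman has a 10% chance of dropping out, the observable rate is 0.9p. At a true 62% this is 0.558, and P(X ≥ 39 | 50, 0.558) is about 0.1%. At a true 80% it is 0.72, and the probability is 22%. Pairing the 39/50 cut-off with this imputation is therefore very strict.

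**The case against.** The strongest reply is that 3a is a hypothesis and not a decision rule. It states an expected rate, and nowhere does the plan say the claim is accepted once the observed proportion passes 62%. That is right. A reader might infer that the sponsor has committed to declaring superiority on a bare point estimate, but the documents do not support this. The 45% and 55% figures are conditional on reading 3a as a comparison of observed rates. What stands is that the plan supplies no other way to judge it.

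Second, the external comparison is declared, the study is called a pilot, and primary goal 2 confines the efficacy comparison to the two strengths. The Section 3 statements on site are background aims. This also stands: using a published benchmark is legitimate, and the absence of a vaginal arm is an open design choice. It does not make a more-efficacious-than conclusion available.

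Third, a reader might infer that the choice of score will inflate the rate. Section 3 notes that not all women with intercourse pain had tampon pain, and inclusion criterion 9 ties intercourse attempts to a tolerable Tampon Test. But the tampon observation comes from a previous study, and a woman with no baseline tampon pain has no moderate or severe tampon score to correct. The modified VPAQ, given at screening and weeks 4 and 12, might also capture penetration pain; its items are not shown. The documents support an unresolved choice, not a bias of known direction or size.

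Finally, the missing cut-off, score and citation would each, alone, be missing detail. They matter here because they feed a comparative claim.

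**Conclusion.** The point holds in limited form. Hypothesis 3/3a is worded as a comparison that the design cannot deliver, and Section 12 provides no analysis for it. Read as an observed rate against 62%, it would be met roughly half the time with no advantage over the benchmark (0.447 at n=50, 0.554 at n=45). Counts of 32 to 38 of 50 would meet it without excluding 62%. These figures assume pooled arms, exact binomial methods and a benchmark free of error. The sampling error of the 62% is not given, and allowing for it would make the comparison less certain still.

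A reader might conclude that the trial's efficacy analysis as a whole is unsound. The documents do not support that. The randomised comparison between strengths is unaffected, and its stated power reproduces. The change should be made, but it concerns what may be concluded from one hypothesis.

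**What to change.** Reword 3/3a as estimation of the correction rate against an external benchmark, and add to Section 12:

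- The pooled proportion corrected at week 12 (Visit 6), with an exact two-sided 95% interval and each arm shown descriptively.
- A statement that the rate exceeds 62% only if the lower limit is above 62%: 39/50, or 35/45 if 45 women are analysed.
- No conclusion of superiority over vaginal therapy, and no attribution of benefit to site or frequency.
- Fixed before any outcome data are reviewed: the NRS definition of correction, which score decides (tampon or intercourse), the denominator and the missing-data rule. Report the alternative denominator as a sensitivity analysis. Counting missing women as not corrected is one option and need not be the default, given how strict it is with the 39/50 cut-off.
- The source of the 62%. Section 3 cites a survey in which 38% of users found estrogen products inadequate, and 100 − 38 = 62, but the plan does not link the two. If that is the origin, it should be said.

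The cost is protocol and SAP wording, with no new data. The sponsor gives up the comparative claim. Power to exceed 62% is low unless the true rate is near 80% or above, so the result will mostly be an estimate with its interval, which is a reasonable product for a pilot.
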